3.1 Intra-patient dose escalation

For patients undergoing intra-patient dose escalation, all data will be summarized and listed by initial treatment group they were assigned to.

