2.1.1.2 Planned/received treatment

- Intended/planned treatment is the first planned treatment reported in the DAR (e)CRF. For combination trial it is the combination of the first planned treatment reported in the DAR (e)CRF of each component of the combination.
- Treatment received is defined as:
 - (i) the treatment assigned if it was received at least once, or
 - (ii) the first treatment received when starting therapy with study treatment if the assigned treatment was never received.

Each patient will be classified into and analyzed consistently within one (and only one) treatment group/arm.

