(Phase II arm 1, if required)*** /	C1D1	± 00:15	01:30 post-dose	C1D1, [01:15, 01:45]
Phase II arm A	C1D1	± 00:30	02:30 post-dose	C1D1, [02:00, 03:00]
	C1D1	± 01:00	05:00 post-dose	C1D1, [04:00, 06:00]
	C1D1	± 01:00	08:00 post-dose	C1D1, [07:00, 09:00]
	C1D2	-03:00	< 00:00 pre-dose	C1D2, [-03:00, 00:00]
	C1D15	-03:00	< 00:00 pre-dose	C1D15, [-03:00, 00:00]
	C1D15	± 00:05	00:30 post-dose	C1D15, [00:25, 00:35]
	C1D15	± 00:15	01:30 post-dose	C1D15, [01:15, 01:45]
	C1D15	± 00:30	02:30 post-dose	C1D15, [02:00, 03:00]
	C1D15	± 01:00	05:00 post-dose	C1D15, [04:00, 06:00]
	C1D15	± 01:00	08:00 post-dose	C1D15, [07:00, 09:00]
	C1D16	- 03:00	< 00:00 pre-dose	C1D16, [-03:00, 00:00]
	C2D1	-03:00	< 00:00 pre-dose	C2D1, [-03:00, 0:00]
every cycle Day 1 (pre-dose), up to Cycle 10, i.e. C3D1, C4D1, . C10D1), i.e. C3D1, C4D1, …,	

Notes:

C = *cycle*, *D* = *Day*, *hh:mm* = *hours and minutes*

00:00 = time of study treatment intake

Assessment	Visit	Time Window	PK assessment time point	Time Window Definition
*** first 10 patients in each	arm only.			

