2.2 Analysis sets

For inclusion in any analysis set it is required that a patient has correctly consented and has received at least one dose of study treatment. For those incorrectly consented patients, they will be excluded from all analysis.

The following analysis sets which will be derived prior to database lock will be used.

Full Analysis Set

The FAS includes all patients who received at least one dose of LGX818 or MEK162 or LEE011. Patients will be classified according to the planned treatment regimen (dose, schedule, tablet variant). The FAS will be used for all listings of raw data. Unless otherwise specified the FAS will be the default analysis set used for all analyses.

Note that patients who were screened and are eligible but never started treatment will not be included in the FAS. This is considered as an acceptable deviation from the ITT principle in the context of the Phase I study in which safety is considered as a primary objective.

The FAS will be used for all listings of raw data. Unless otherwise specified the FAS will be the default analysis set used for all analyses. Patients will be analyzed according to the planned treatment regimen.

Safety Set

The safety set includes all patients who received at least one dose of LGX818 or MEK162 or LEE011, and have at least one valid post-baseline safety assessment. The statement that a patient had no AEs (on the AE eCRF) constitutes a valid safety assessment.

Patients will be classified according to treatment received (See Section 2.1.1.2).

Dose Determining Set (DDS)

The dose-determining set (DDS) includes all Phase Ib patients from the safety set who either completed a minimum exposure requirement and have sufficient safety evaluations or discontinued prematurely due to a dose limiting toxicity (DLT).

A patient is considered to have met the minimum exposure requirement if having received at least 75% of the planned combination doses (i.e. 21 out of 28 planned daily doses for QD or BID, 11 out of 14 planned doses for an every other day dosing schedule, and 16 days out of 21 days for 3 week on, 1 week off dosing schedule) of study treatment within the first Cycle of dosing. The length of a cycle is 28 days.

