3.3.1.4 Dose change

Dose delay/interruption: any dose change/delay flagged in the DAR CRF page, satisfying the following criteria:

- a reason other than "as per protocol",
- a zero actual dose,
- occurs between the first and last non-zero doses,
- follows a non-zero actual dose.

Dose reduction: any dose change/delay flagged in the DAR CRF page, satisfying the following criteria:

- a reason other than "as per protocol",
- a non-zero actual dose below the immediate previous non-zero actual dose
- a non-zero actual dose below the treatment assigned as per safety set

Dose increment: any dose change/delay flagged in the DAR CRF page, satisfying the following criteria:

- a reason other than "as per protocol",
- a non-zero actual dose above any previous non-zero actual dose
- a non-zero actual dose above the treatment assigned as per safety set

The following criteria are used to identify an intra-patient dose escalation:

- dose change flag checked with reason "as per protocol"
- planned dose above any previous planned dose.

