3.7 Pharmacokinetic data

3.7.1 Descriptive statistics

PK concentration data will be listed and summarized in the interim CSR. PK concentration data will be summarized in the final CSR but not listed.

Plasma concentrations that were excluded for the derivation of PK parameters and labeled as such in the listings will also excluded from the summary statistics.

The PK parameters defined in Table 3-5 will be calculated as appropriate. Steady state (SS) is assumed to be reached on Day 15 and the patient should have taken all scheduled doses for at least 2 consecutive days prior to Day 15. The PK parameters will be listed and summarized using relevant statistics in the interim CSR. The PK parameters will be summarized in the final CSR but not listed. Median, minimum, and maximum will be calculated for tmax and tlast. For other PK parameters, mean, standard deviation, CV% mean, geometric mean, CV% geo-mean, median, minimum, and maximum will be calculated. In addition, in case drug accumulation is observed upon multiple dosing, additional PK parameters describing drug accumulation will be added to the analysis (i.e. effective half-life).

Only PK blood samples with date and time and for which at last prior dose dates and times are adequately recorded will be included in the PK analyses. Samples taken from patients who vomited within 4 hours of dosing will be excluded from the analysis. The FAS will be used.

Table 3-5	Definition of PK parameters	
Parameter	Definition	
Cmax	Maximum observed plasma concentration after drug administration [mass x volume- 1]	
Tmax	Time to reach Cmax [time]	
Ctrough	Predose plasma concentration before drug administration [mass x volume-1]	

AUClast	Area under the concentration-time curve from time zero to the last measurable				
T 14	concentration sampling time (tlast) [mass x time x volume-1]				
Tlast	Time at which the last measurable concentration was observed [time]				
AUCinf	Area under the concentration-time curve from time zero to infinity with extrapolation of the terminal phase [mass x time x volume-1]				
AUCtau	Area under the concentration-time curve from time zero to tau after first dose [mass x time x volume-1]				
AUC(0-t)	Area under the concentration-time curve from time zero to time t after first dose [mass x time x volume-1]				
AUC(0-t), ss	Area under the concentration-time curve from time zero to time t after drug administration at steady state [mass x time x volume-1]				

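### Phase Ib PK samples drawn after a dose change, mainly pre-dose samples from C2D1 to C10D1, are summarized under a dose the patient was no longer taking

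*SAP*

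**What the plan says.** Four rules in the SAP together decide which row a concentration goes into.

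- Section 3.1: "For patients undergoing intra-patient dose escalation, all data will be summarized and listed by initial treatment group they were assigned to".
- Section 3.7.1, on PK: "Samples taken from patients who vomited within 4 hours of dosing will be excluded from the analysis. The FAS will be used".
- Section 2.2, on the FAS: "Patients will be classified according to the planned treatment regimen (dose, schedule, tablet variant".
- Section 2.1.1.2: "Each patient will be classified into and analyzed consistently within one (and only one) treatment group/arm". The same section defines planned treatment as the first planned treatment on the dosing record.

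On sampling, the PK window table in section 2.1.2.9 has full profiles on C1D1 and C1D15, then a pre-dose sample at C2D1 and "every cycle Day 1 (pre-dose), up to Cycle 10".

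On dose changes, section 3.3.1.4 defines a dose reduction. It also defines an intra-patient escalation, one criterion for which is a "planned dose above any previous planned dose".

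On steady state, section 3.7.1 assumes it is reached on Day 15 and adds that "the patient should have taken all scheduled doses for at least 2 consecutive days prior to Day 15".

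**The concern.** Keeping a patient in the initial or planned group is a conventional choice for efficacy and disposition. A plasma concentration is different, because it reflects the dose taken before the sample. If that dose differs from the row label, the row mixes exposures from different doses.

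The single and multiple dose PK profile is a Phase Ib secondary objective (Table 1-1), and section 1.1 names PK among the inputs to dose-escalation decisions. The rows most at risk are small, so a few samples at another dose can move a mean visibly. In the final CSR, which reports the triple combination, section 3.7.1 has PK summarized but not listed. A reader of that report would have no PK listing from which to re-sort samples by actual dose.

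**Working it through.** The SAP gives no figure on this point, so the check sets its rules side by side and then illustrates the size.

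**Step 1. Which row does a sample taken after a dose change enter?**
- Escalation: section 3.1 answers directly. All data stay in the initial group.
- Reduction: section 3.1 is silent. The answer comes from 3.7.1 (FAS), 2.2 (planned regimen) and 2.1.1.2 (one group per patient), and it is again the original row.
- Moving PK to the Safety Set would not help. Section 2.1.1.2 defines treatment received as the assigned treatment if it was received at least once.

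**Step 2. Which outputs are exposed?**
- Phase Ib concentration tables (section 4.1.1, Tables 14.4.4.1.1, 14.4.4.2.1, 14.4.4.3.1, 14.4.4.4.1 and 14.4.4.5.1) are by treatment group, and their titles set no Cycle 1 limit. The pre-dose samples from C2D1 to C10D1 are the main exposure.
- Parameter tables are by profile day, and full profiles exist only on C1D1 and C1D15. AUCtau,ss and Cmax,ss are affected only by a change before Day 15. The same holds for the accumulation ratio AUCtau,ss/AUCtau, which would be halved under dose proportionality if the dose were halved between the two profiles.
- Mean concentration-time figures are limited to Cycle 1 (section 4.1.3).
- Phase II PK tables are by arm, so their rows do not carry a dose label in the same way.

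**Step 3. Does an existing rule remove these samples?**
- Recorded sample and prior-dose times, and the vomiting rule: neither refers to the dose level.
- Concentrations excluded from parameter derivation are also dropped from the summaries (3.7.1). This allows removal sample by sample, but no criterion ties it to a dose that differs from the group's.
- The steady-state condition speaks of scheduled doses over at least 2 days before Day 15. It does not say that these must be the group's dose, and it does not cover later pre-dose samples.
- The repeat analysis without patients on an inappropriate dosage is optional and belongs to the models in 3.7.2.

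**Step 4. Illustrative size.** Inputs: n = 3 to 6, the cohort size in 2.1.1.1; k = 1 patient off the labelled dose; r = dose taken divided by labelled dose. Assumptions: troughs proportional to dose, and patients otherwise equal.

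Arithmetic mean ratio = ((n − k) + k·r)/n. Geometric mean ratio = r^(k/n).

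| r | n | Arithmetic | Geometric |
|---|---|---|---|
| 2 | 3 | (2 + 2)/3 = 1.33 | 2^(1/3) = 1.26 |
| 2 | 6 | (5 + 2)/6 = 1.17 | 2^(1/6) = 1.12 |
| 0.5 | 3 | (2 + 0.5)/3 = 0.83 | 0.5^(1/3) = 0.79 |
| 0.5 | 6 | (5 + 0.5)/6 = 0.92 | 0.5^(1/6) = 0.89 |

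A treatment group may pool several cohorts. With k = 1 the arithmetic shift is (r − 1)/n, so it shrinks as n grows; it grows when few patients remain at a late cycle. Grouping by dose taken makes the ratio 1.00 under these assumptions.

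**The case against.** The strongest reply is that the reach is narrow. The exposed outputs are descriptive and secondary, and no decision rule is attached to late pre-dose summaries. Cmax, AUC, half-life and clearance come from Cycle 1 profiles and are untouched by a later dose change. The route for excluded concentrations lets the pharmacokineticist drop a sample. The word scheduled in the steady-state condition is undefined and could mean the originally planned dose. For the dual combination, the interim CSR lists PK concentrations and parameters, so re-sorting is possible there. All of this stands, and it confines the point mainly to Phase Ib pre-dose summaries after Cycle 1. It does not supply a rule that puts those samples in the right row.

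A reader might infer three stronger things that the SAP does not support.
- That exposure at the MTD/RP2D is understated. The direction depends on the mix of escalations and reductions in that group, which is not given. The relative dose intensity categories do not settle it, because they cover the whole exposure period and reflect interruptions as well as reductions.
- That the dose-exposure relation is flattened. Section 3.7.2 models AUCtau,ss and Cmax,ss on log(dose), not on the group label, and does not say whether that dose is planned or actual. Bias in the slope is possible but not shown.
- That Table 1-1 promises a PK profile by dose. It refers to single versus multiple dosing.

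**Conclusion.** The point holds for Phase Ib. As written, the rules file pre-dose concentrations taken after an escalation or reduction under a dose the patient was not taking, and no exclusion criterion tied to dose corrects this. C1D15 parameters and the accumulation ratio share the problem only for changes before Day 15.

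Under dose proportionality and otherwise equal patients, one patient at double the labelled dose in a group of 3 to 6 shifts the arithmetic mean trough by +33% to +17%, and one at half by −17% to −8%. These figures show sensitivity; they do not estimate the bias in this trial, because the SAP gives neither the number nor the timing of dose changes. The correction should be made because it replaces a stated rule unsuited to concentration data and needs no new data.

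**What to change.** Add to section 3.7.1, as an explicit exception to section 3.1 and to FAS planned-regimen grouping, one of two rules for Phase Ib PK concentrations and parameters:

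1. summarize them by the dose of that drug actually taken at sampling, from the DAR eCRF; or
2. keep the planned group, but exclude samples taken after a dose change from the group summary and flag them.

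Under either rule, summarize a steady-state value only if the dose was unchanged over the qualifying period before the sample. In section 3.7.2, state that log(dose) is the actual dose. The change concerns the grouping of results only and touches no dosing rule.

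The cost is SAP wording and a merge of PK data with dosing records, which are already collected (section 4.1.2 lists them by drug). The downside is smaller or uneven n per row at late visits.

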3.2 Patient disposition, background and demographic characteristics

Demographic and other baseline data, including disease characteristics, will be summarized descriptively by treatment group in Phase Ib and patient group in Phase II using the FAS.

3.2.1 Patient disposition

The number of patients who were enrolled and treated, as well as those who completed or discontinued treatment or the study (along with their reasons for premature discontinuation), or were still ongoing at the time of the analysis will be summarized. If treatment discontinuation or study evaluation completion due to COVID-19 is reported for any patients,

Version 2.2

this will also be included in the summary. A listing of study completion by treatment will be produced. Patients are considered to be ongoing if they have not discontinued due to any reason (e.g., disease progression, AE, withdrawn consent).

Baseline demographic, reasons for screen failure and serious adverse events will be listed for screened failure patients.

3.2.2 **Protocol deviations**

All protocol deviations will be finalized before database lock. This study was previously under the sponsorship of Novartis and transitioned to Pfizer sponsorship with PPD oversite, but protocol deviations are still coded according to the Novartis VAP Module 3. Protocol deviations and reasons for exclusion from populations will be tabulated. The number and percentage of patients in the FAS with any protocol deviations will be tabulated by the deviation category (as specified in the Novartis VAP Module 3 documents) and within each deviation category, deviations due to COVID-19 will also be summarized. All protocol deviations will be listed.

3.2.3 Background and demographic characteristics

Background and demographic characteristics including age, gender, race, ethnicity, height, weight, WHO performance status, tumor type, medical conditions, BRAF mutation status, geographic region and LDH, etc. will be listed and summarized using descriptive statistics. The summaries will be based on the assessments from the screening visit (baseline).

In addition, the following derived variables derived from the demographic (e)CRF will be described:

- age groups summarized by class (<65, ≥ 65 years)
- weight summarized by class ($<55, 55-75, \ge 75$ kg)
- Body mass index (BMI) calculated as weight/(height**2) (kg/m²) where weight is measured in kg and height in m
- The body surface area (BSA) is calculated using Gehan and George formulae: BSA [m²] = 234.94*(height[cm]**0.422)*(weight[kg]**0.515)/10000

3.2.4 Medical History

Past and current medical history will be summarized and listed. Separate summaries will be presented for current and past historical medical conditions; these summaries will be presented by primary system organ class and preferred term. Medical history/current medical conditions will be coded using Medical Dictionary for Regulatory Activities (MedDRA) version 18.1.

3.2.5 **Prior antineoplastic therapy**

Prior anti-neoplastic therapies will be listed, and the latest therapy will be summarized in three separate tables for surgery (procedure, residual disease for non-biopsy surgery), radiotherapy (location, setting and best overall response) and medications (therapy type,

setting, previous treatment with selective BRAF inhibitor and best overall response). In addition, the time between end of last therapy and start of treatment will be summarized.

Last surgery is derived based on procedure date. Last radiotherapy is derived based on end date. Last treatment is derived based on the last end date of any of the components of the regimen.

The summary of prior anti-neoplastic medications will be presented by Anatomical Therapeutic Chemical (ATC).

3.2.6 Diagnosis and extent of cancer

Diagnosis and extent of cancer will be listed and the summarized by number (%) of patients in each of the categories for the following variables: primary site of cancer (includes melanoma type and subtype), details of tumor histology/cytology, histological grade, stage at initial diagnosis, current stage of cancer, current extent of disease (metastatic sites), and types of lesions at baseline.

In addition, the following continuous and categorized time intervals will be computed and summarized:

- Time since initial diagnosis to first dose of study drug, calculated as (date of study treatment start date of initial diagnosis of primary site + 1)/30.4375. The following categories will be used: <6 months, ≥6 to <12 months, ≥12 to <24 months, ≥24 months
- Time since initial diagnosis to first relapse, calculated as (date of first relapse date of initial diagnosis of primary site + 1)/30.4375. The following categories will be used: <6 months, ≥6 to <12 months, ≥12 to <24 months, ≥24 months
- Time since initial diagnosis to most recent recurrence/relapse, calculated as (date of most recent recurrence/relapse date of initial diagnosis of primary site + 1)/30.4375. The following categories will be used: <6 months, ≥6 to <12 months, ≥12 to <24 months, ≥24
- Time since most recent recurrence/relapse to first dose of drug, calculated as (date of study treatment start date of most recent recurrence/relapse + 1)/30.4375. The following categories will be used: <1 month, ≥1 to <2 months, ≥2 to <3 months, ≥3 months

See Section 2.1.2.10 for handling partial missing dates for the intervals.

3.2.7 Other baseline characteristics

All data collected during the baseline evaluation, including child bearing potential, pregnancy test results, and exploratory biomarker informed consent will be listed.

3.3 Treatments (study drug, rescue medication, other concomitant therapies, compliance)

3.3.1 Study medication

Exposure will be summarized overall in terms of:

• The duration of study treatment exposure,

- The cumulative dose,
- The dose intensity (DI) and/or relative dose intensity (RDI)
- The percentage of actual days dosed during the treatment period for daily dosed compounds
- The percentage of days received planned doses during the treatment period for daily dosed compounds (calculated for Phase II subjects only)

Exposure will be summarized on the Safety Set. For bid regimen, note that if interruption is after a one day reduction, this one day reduction will be considered as start of interruption and not as reduction.

3.3.1.1 Duration of study treatment exposure

The following algorithm will be used to compute the duration of study treatment exposure for patients who took at least 1 dose of any of the components of the study treatment:

Duration of exposure (days) = (last date of exposure to any study treatment component) – (date of first administration of any treatment component) + 1.

Both date of first administration of study treatment and last date of exposure to study treatment are defined in Section 2.1.2.3 and Section 2.1.2.5, respectively.

For patients who did not take any drug the duration of drug exposure is by definition equal to zero.

3.3.1.2 Cumulative dose

The actual cumulative dose for each study drug is defined as the total dose for this study drug given during the study drug exposure and is expressed in mg. For patients who did not take any of the drug, the actual cumulative dose is by definition equal to zero.

The planned cumulative dose is defined as the total dose planned to be given during the study treatment exposure and is expressed in mg.

3.3.1.3 Dose intensity and relative dose intensity

The dose intensity (DI) for patients with non-zero duration of exposure is defined as follows:

Planned dose intensity (PDI) (mg/day) = planned cumulative dose (mg) / planned number of days patient should have taken the drug (days)

Actual dose intensity (ADI) (mg/day) = actual cumulative dose (mg) / planned number of days patient should have taken the drug (days)

For patients who did not take any drug the ADI is (by definition) equal to zero.

ADI and PDI will be expressed in mg/day for LGX818, MEK162 and LEE011.

Relative dose intensity (RDI) = ADI (mg/day) / PDI (mg/day).

For patients who did not take any drug the actual RDI is (by definition) equal to zero.

The ADI and RDI will be summarized separately for each of the study treatment components by using the duration of the study treatment exposure, not the duration of each of the components.

The RDI for each of the study treatment components will be presented also with the following categories: <0.5, ≥ 0.5 to <0.75, ≥ 0.75 to <0.9, ≥ 0.9 to <1.1 and ≥ 1.1 .

Dose intensity for the first cycle or by cycle can be computed using cycle length definition (see Section 2.1.2.6) as exposure periods.

